## 1.0 Study Summary

Study Title	HMH Omega-3 Covid Recovery Study
Study Design	We will conduct a two-arm, double blind randomized 12-week study to supplement omega-3 (EPA + DHA) among 100 adults (age 18+) who had covid-19 and are experiencing possible after-effects from the illness (post-acute sequelae of covid-19, also called post-covid syndrome or long covid syndrome).
Primary Objective	The primary objective is to serve as a feasibility study for omega-3 fatty acid supplementation v. placebo in adult patients to limit long covid syndrome. This will serve as a proof-of-concept for a larger follow-up study to subsequently be conducted.
Secondary Objective(s)	Determine which of the post-covid symptom(s) are most impacted by omega-3 supplement.
Research Intervention(s)/Investigational Agent(s)	Participants will be assigned to one of two study arms and asked to take an Omega-3 supplement or placebo for 12 weeks. Participants will report symptoms bi-weekly throughout the study period. A spot blood sample to assess omega-3 levels will be done at baseline and at the end of the 12-week study period.  A survey will be used bi-weekly to assess health status and outcomes via patient self-report. Data on demographics and comorbidities such as obesity and diabetes will be collected at baseline. At the end of study participation, subjects will take a follow-up survey assessing feasibility.
IND/IDE #	IND # 157250
Study Population	Hackensack Meridian Health team members age 18+ who tested positive for COVID-19 28+ days prior and who are not already taking an Omega-3 supplement.
Sample Size	50 participants in each arm = 100 total for final analysis (up to 60 participants in each arm will be recruited if needed, dependent on attrition for a total of up to 120)
Study Duration for individual participants	Individual participants will be in the study for 12 weeks. During the 12 week study period, subjects will be sent a survey every two weeks. At the end of the 12 weeks, subjects will complete a short survey collecting feasibility and acceptability data.
Study Specific Abbreviations/Definitions	
 
• Hackensack Meridian Health (HMH)
 
• Center for Healthy Senior Living (CHSL)
 

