#### **6.2 Research Procedures**

For an overview of the study, please see figure 1 below.

1. Team members who email the study team at the address on the flyer will be sent an eligibility survey in REDCap to determine if study inclusion criteria are met.
2. Those who meet study inclusion criteria will then be sent the study consent form in REDCap, and encouraged to call or email the study team with questions.

3. If the patient expresses further interest in study participation, s/he will be consented via REDCap and then will be sent a link to the baseline survey in REDCap.
4. Upon consent, RC will assign ID# and enter the subject into REDCap (study data management system).
5. Subjects will be randomly assigned to receive 3 Omega-3 (EPA+DHA) mini-capsules twice daily (total of 2,100mg per day) for 12 weeks in the experimental intervention arm or three placebo mini-capsules twice daily for 12 weeks.
  - Study supplement or placebo are supplied at no cost to the subject and will be mailed to the subject's home.
  - Study subjects will receive two shipments over the course of study participation.
    - Package 1 upon enrollment
    - Package 2 at the end of week 4
  - Subjects will also receive, in these shipments, two spot blood sample tests for omega-3 levels, and directions indicating when to use the test kits.
6. All study subjects in each arm will be asked to give a spot sample (2 drops) of blood at baseline and again after 12 weeks (end of study participation). This will be done using OmegaQuant test kits that are mailed to the subject's home. The de-identified samples will be mailed by the subject in the provided envelope to OmegaQuant Lab, associated with University of South Dakota Medical Center, for analysis of omega-3 levels. These tests involve no cost to the subject. Subjects will be informed of their omega-3 level after results are returned from the lab and the subject's participation in the study is complete.
7. Monitoring of Subjects:
  - Subjects will be encouraged to call RC at any time with study questions. RC will also call each subject weekly to ensure procedures are being followed and answer any questions. The weekly "check-in call" will occur for 12 weeks.
  - Each subject will be checking their blood pressure. Subjects will report their blood pressure via REDCap in their bi-weekly survey. Reported adverse events will be documented.

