## 10.0 Inclusion and Exclusion Criteria

### Inclusion Criteria

- Team member at Hackensack Meridian Health
- Age: 18+
- Willing to provide informed consent
- Formal diagnosis of COVID-19 via PCR test (if home test was done, team member must confirm via PCR test)
- Outpatient treatment only for covid-19; no hospitalization (most team members will be vaccinated and may likely have milder case)
- Must be experiencing 1+ ongoing covid-19 symptom being measured in this study (respiratory symptoms (shortness of breath, cough), fatigue, loss of taste, loss of smell)
- Symptom(s) have persisted for more than 12 weeks after initial infection

- Symptom(s) coincided with covid-19 infection and were not present prior to covid-19 infection
- Does not have soy allergy
- Does not have allergy to fish
- Able to participate in bi-weekly surveys in REDCap
- Able to take own blood pressure and record it in bi-weekly REDCap survey
- Willing to participate in 12-week study and be assigned to either intervention or placebo arm
- Not currently taking an omega-3 supplement or other high-dose supplement (over 2,000 IU) with potential for aiding recovery of long covid syndrome (e.g. zinc, Vit C, Elderberry).
- Able to take/swallow six mini-pills daily
- Able and willing to give a spot blood sample (2 drops) at baseline and end of study.

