## **12.0 Local Number of Subjects**

The number of subjects will be 50 in each of two arms, for a total of 100 subjects for analysis. Up to 60 participants in each arm will be recruited if needed, dependent on attrition, for a total of up to 120 subjects.

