## Inclusion/Exclusion Eligibility Survey

Please complete the survey below.

Thank you!

---

1. Are you a team member at Hackensack Meridian Health?  Yes  No

---

2. Are you age 18 or over?  Yes  No

---

3. Have you tested positive for coronavirus (COVID-19) via PCR test? (Note: home test or other rapid test MUST be confirmed by a PCR test)  Yes  No

---

4. On what date were you diagnosed with Covid-19 via PCR test? \_\_\_\_\_

---

5. Have you been experiencing symptom(s) related to covid-19 for more than 12 weeks after initial infection?  Yes  No

---

6. Which of the ongoing covid-19 symptoms have you been experiencing? (please check all that apply)  Respiratory symptoms (shortness of breath and/or cough)  Fatigue  Loss of taste  Loss of smell

---

7. Were any of these symptoms present before your covid-19 infection?  Yes  No

---

8. Where you ever hospitalized for covid-19?  Yes  No

---

9. Did you require supplemental oxygen for covid-19?  Yes  No

---

10. Do you have a known soy allergy?  Yes  No

---

11. Do you have a known allergy to fish?  Yes  No

---

12. Are you able to take an online survey every other week (bi-weekly) for the study?  Yes  No

---

13. Are you able to take your own blood pressure and record it in bi-weekly online survey?  Yes  No

---

14. If you qualify, are you willing to participate in this 12-week study and be assigned to either intervention or placebo arm? This means you will be assigned to either take the omega-3 supplement or a placebo (pill with soybean oil in it).  Yes  No

Confidential

Confidential

Page 2

15. Are you currently taking an omega-3 supplement or other high-dose supplement (over 2,000 IU) with potential for aiding recovery of long covid syndrome (e.g. zinc, Vit C, Elderberry)?

 Yes No

16. Are you able to take/swallow six mini-pills daily?

 Yes No I don't know

17. Are you able and willing to give a spot blood sample (2 drops) at the beginning (baseline) and end of the study?

 Yes No

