**Please select which week you stopped experiencing the symptoms described below.**

**If you never experienced this symptom, please select N/A**

	During the first two weeks since my covid-19 diagnosis	During the third week since my covid-19 diagnosis	During the fourth week since my covid-19 diagnosis	I still experience this symptom	N/A - I never experienced this symptom
Shortness of breath					
Cough					
Fatigue					
Lack of taste					
Lack of smell					
Other					

If you answered "Other," please specify/describe additional symptom #1: \_\_\_\_\_

If you answered "Other," please specify/describe additional symptom #2: \_\_\_\_\_

If you answered "Other," please specify/describe additional symptom #3: \_\_\_\_\_

Comment - Optional (please add here anything else you might want to share with us regarding any symptoms and/or your quality of life since your covid-19 diagnosis) \_\_\_\_\_

Please write-in your blood pressure, taken anytime in the last 2 weeks: \_\_\_\_\_

Source of blood pressure (BP) equipment and method:

- BP was taken by machine at home
- BP was taken by machine at a pharmacy
- BP was taken manually in medical office

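### The protocol gives conflicting eligibility windows (28 days since a positive test in one place, more than 12 weeks of symptoms as both inclusion and exclusion in another), and no rule uses the PCR date collected at screening to check them

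*Combined protocol and SAP*

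**What the plan says.** In the Study Summary (1.0), the Study Population row reads "Hackensack Meridian Health team members age 18+ who tested positive for COVID-19 28+ days prior and who are not already taking an Omega-3 supplement". The Study Design row adds that subjects have possible after-effects of the illness, again with no minimum duration.

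The inclusion list in Section 10.0 requires "Symptom(s) have persisted for more than 12 weeks after initial infection". Its PCR criterion sets no minimum time since the test. The exclusion list in Section 10.0 contains the same 12-week sentence, word for word and not negated, although the lines around it are negated versions of their inclusion counterparts.

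Section 6.2 makes the Appendix A survey the screening step: people who email the study team "will be sent an eligibility survey in REDCap to determine if study inclusion criteria are met", and only those who meet the criteria are sent the consent form. Item 4 of that survey asks "On what date were you diagnosed with Covid-19 via PCR test", with no cut-off. Item 5 asks "Have you been experiencing symptom(s) related to covid-19 for more than 12 weeks after initial infection", to be answered yes or no. Appendix A does not say which answer qualifies.

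The bi-weekly survey in Appendix C asks in which week each symptom stopped. Its last dated choice is "During the fourth week since my covid-19 diagnosis". After that come only a choice for symptoms still present and a not-applicable choice.

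**The concern.** Time since infection is the main feature that separates slow recovery from a persistent syndrome. The Background (3.0) says that after-effects last several weeks in some people and several months in others. A plan that gives different windows in different places leaves open which patients the study describes.

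Three uses of the data depend on the answer. The study is meant as proof of concept for a larger trial, so its screening yield and recruitment rate will be carried forward, and both depend on how wide the window is. Section 17.1 compares the arms on symptom recovery, and the chance of recovering without treatment plausibly depends on how long symptoms have already lasted. Section 4.2 takes the symptom analysis from Appendix C, whose week choices are counted from diagnosis and must suit the people enrolled.

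The screening step is also thin. Conduct is remote, and the protocol describes no check of symptom duration against a record. The one date that could serve as a check is collected and then not used by any stated rule.

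**Working it through.** The documents give no figure to reproduce here, so the check is a comparison of the windows.

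**Inputs.** 12 weeks x 7 = 84 days. Four weeks x 7 = 28 days.

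| Place | Clock starts at | Window as written |
|---|---|---|
| 1.0 Study Summary | positive test | day 28 onward; no symptom duration |
| 10.0, inclusion list | initial infection | symptoms beyond day 84 required |
| 10.0, exclusion list | initial infection | symptoms beyond day 84 excluded |
| Appendix A, item 4 | PCR test, infection not specified | no cut-off |
| Appendix A, item 5 | initial infection | beyond day 84, yes/no; qualifying answer not stated |
| Appendix C | diagnosis | last dated choice ends at day 28 |

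**Combining the lines** (one infection, test close to onset):

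1. Summary with inclusion list: day 28 onward and beyond day 84 together give beyond day 84. The 12-week group lies inside the Summary population.
2. Summary with exclusion list: day 28 onward, minus everyone beyond day 84, leaves days 28 to 84. The width is 84 - 28 = 56 days, or 8 weeks. This window does not overlap the one in step 1.
3. Inclusion list with exclusion list: beyond day 84 is both required and excluded. Read literally, nobody is eligible.

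The answer to item 5 that admits an applicant therefore depends on which list is applied: yes under the inclusion list, no under the exclusion list.

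**Appendix C.** Under the same simplification, someone who enters after day 84 and then loses a symptom does so in week 13 or later. No dated choice covers that, since the dated choices stop at day 28. A subject entering at exactly day 28 would also be past the last dated choice by the first survey two weeks later (28 + 14 = 42). So Appendix C does not fit the 12-week rule, and it is not good evidence that a 28-day rule was intended either.

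**Items 4 and 5.** Item 4 does not name the infection, while item 5 refers to the initial one. Section 6.2 recognises that repeat infection occurs. Suppose an applicant was infected long ago and again 6 weeks ago, and the PCR belongs to the second episode. Item 4 then shows 6 x 7 = 42 days. If the applicant reads item 5 as counting from the first infection, the answer may be yes. The study would hold a 42-day date beside a claim of more than 84 days, and no rule would bring the two together.

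**The case against.** The strongest reply is that the Summary line is only a loose synopsis. It also leaves out the PCR requirement, the bar on hospitalised cases, the four qualifying symptoms and the allergies, and nobody would read those gaps as separate routes into the study. The inclusion list and item 5 agree on 12 weeks, and Section 6.2 says the survey tests the inclusion criteria. Much of this stands.

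A reader might infer from the mismatch that two different populations can be enrolled. The documents do not support that. An applicant between days 28 and 84 with a single infection, answering truthfully, says no to item 5 and fails the inclusion rule. The conflict lies in how the population is described and in how the rule is coded; it has not been shown to open a second way in.

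A reader might also infer that a late confirming PCR admits the wrong people. It does not. The duration rule counts from infection, so someone with more than 12 weeks of symptoms and a later PCR meets it.

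The reinfection case is weaker than it first looks, because item 5 asks how long symptoms have been present, and someone whose symptoms began six weeks ago should say no. The ambiguity is real, but the documents say nothing about how often it would arise.

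Finally, the endpoint in Section 4.1 is feasibility and acceptability from Appendix D, and Section 17.1 says the study is not powered. That limits the stakes. It does not remove them, because Section 17.1 also names the comparison of recovery as the primary analysis. Nor does the synopsis defence deal with the un-negated exclusion line, which sits in the detailed criteria themselves.

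**Conclusion.** The inconsistency holds on the wording alone. The protocol states a 28-day window since a positive test, a 12-week symptom duration as an inclusion criterion, and the same 12-week duration as an exclusion criterion. The gap between the limits is 56 days. Appendix C does not fit people beyond 12 weeks. The window rests on one self-reported yes/no that is not compared with the date collected beside it.

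The effect on results cannot be sized. The documents give no distribution of time since infection among applicants and no recovery rates, so neither the share of subjects affected nor any change in background recovery can be computed. A reader might infer that early entrants would dilute the difference between the arms. That would need recovery rates and a treatment effect by time since infection, and the plan supplies neither. For scale only: with 50 per arm planned for analysis, each subject admitted under the wrong window is 1/50 = 2% of an arm.

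The point should be settled before the screening survey is used. It does not show that the comparison between arms is biased, and it takes no position on which window is right.

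**What to change.** Reconcile the Study Population row in 1.0, both lists in Section 10.0, items 4 and 5 of Appendix A, and the cessation choices in Appendix C to one window with one stated starting point. State which answer to item 5 qualifies.

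Reword item 4 to ask for the PCR date of the infection to which the current symptoms are attributed. Have REDCap flag any applicant whose item 4 date is inconsistent with the answer to item 5. The coordinator then reviews the date of infection or symptom onset before the consent form is sent.

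The check should flag and not reject. A fixed 84-day limit on the PCR date would add a new criterion and turn away people who meet the inclusion rule as written. For example, someone infected 90 days ago by home test, with a confirming PCR 10 days later, has a PCR date only 90 - 10 = 80 days old.

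The cost is a few text edits, one REDCap comparison, and a short review of flagged applicants, some of whom will wait a little longer for the consent form. The check does not prove that symptoms persisted; that still rests on self-report.

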### **6.0 Procedures Involved**

#### **6.1 Study Design**

This is a double-blind, randomized controlled trial (RCT) with two treatment arms:

Arm 1 - Omega-3 (EPA+DHA) – Dose is 2,100mg per day via 3 mini-capsules, 2x/day (a total of 6 mini-capsules per day). Each capsule has 252mg of EPA and 102mg of DHA.

Support for dosing:

- The American Heart Association (AHA) says taking up to 3 grams of fish oil daily in supplement form is considered safe [33]
- Up to 5,000mg of omega-3 fatty acids per day is considered safe [34].
- The U.S. Food and Drug Administration recommends consuming no more than 3 g/day of EPA and DHA combined, including up to 2 g/day from dietary supplements.[35]

Arm 2 - Placebo – made from soybean oil (same dosing schedule as intervention arm)

Supplement and placebo will be supplied by KD Pharma.

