#### **14.0 Withdrawal of Subjects**

If a subject needs to be withdrawn from the study without their consent for medical reasons or non-compliance, she or he will be notified by [name] or [name] by phone, with a follow-up letter mailed to the subject's home.

If a subject chooses to withdraw from the study, she or he must notify the PI by calling the phone number on the consent form. All data collected up to the point of termination will be kept in the study.

Any subject missing both daily doses 3 times a week for 3 weeks in a row will be removed from the study for non-compliance, and asked to dispose of any unused study supplement/placebo.

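### The trial is sized on 100 subjects left for analysis, removes non-compliers after randomisation and names no analysis set, so the recovery comparison would rest on those who remain

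*Combined protocol and SAP*

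**What the plan says.** The sample-size row of Section 1.0 reads "50 participants in each arm = 100 total for final analysis", followed by the allowance that "up to 60 participants in each arm will be recruited if needed, dependent on attrition for a total of up to 120". Section 12.0 says the same: "The number of subjects will be 50 in each of two arms, for a total of 100 subjects for analysis", then "Up to 60 participants in each arm will be recruited if needed, dependent on attrition, for a total of up to 120 subjects".

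Section 14.0 (also 6.2) adds an exclusion that happens after randomisation: "Any subject missing both daily doses 3 times a week for 3 weeks in a row will be removed from the study for non-compliance". On subjects who withdraw, Section 14.0 says "All data collected up to the point of termination will be kept in the study". It does not say whether those data enter the comparison of arms.

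Section 17.1 makes a chi-square or Fisher's exact test on recovery from long-covid symptoms the primary analysis, with significance at p of 0.05 or less. It names no analysis set (all randomised, per-protocol or other), no time point for recovery and no rule for a missing outcome. No section gives an expected dropout rate, defines attrition, or says what triggers the extra recruitment.

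**The concern.** If every randomised subject were analysed, attrition would not change the number analysed, and there would be no reason to recruit 120 to obtain 100. The sizing therefore points to a comparison from which dropouts have gone, and nothing in Section 17.1 corrects that reading.

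Randomisation makes the arms comparable at entry. It does not do so for those still present at week 12. Section 15.0 lists diarrhoea and reflux among the possible effects of omega-3, so intolerance could drive exits in one arm while recovery or lack of benefit drives them in the other. Removal for non-compliance also depends on behaviour that treatment can influence. A difference between arms could then appear, or disappear, because of who left. This matters for a proof-of-concept study whose symptom result is meant to inform a larger trial. Retention is also a feasibility result in its own right, and the plan does not commit to reporting it over all randomised subjects.

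**Working it through.** **Inputs from the documents.** 50 per arm and 100 in total for analysis; up to 60 per arm and 120 in total recruited (1.0, 12.0); threshold 0.05, chi-square or Fisher's exact test (17.1). The documents give no dropout rate, recovery rate or power, so those used below are assumptions.

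**The plan's own figures.** 2 × 50 = 100 and 2 × 60 = 120, so the sums agree. The number 100 cannot be re-derived, because no effect size or power is stated.

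**Attrition implied by the ceiling.** 1 − 100/120 = 1 − 50/60 = 16.7%. As a check, 100/(1 − 1/6) = 120. At 20% attrition the ceiling would have to be 100/0.80 = 125.

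**Chance that the ceiling is enough** (independent dropouts, the same rate in both arms, binomial):

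| Assumed dropout | At least 100 of 120 overall | At least 50 of 60 in both arms |
|---|---|---|
| 10% | 99% | 93% |
| 15% | 74% | 51% |
| 16.7% | 56% | 34% |
| 20% | 21% | 10% |

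**What leaving out dropouts can do.** Assume 60 randomised per arm, no true effect, and 30% recovery, so 18/60 in each arm. Each arm loses 10.

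- Omega-3 loses 10 who had not recovered: 18/50 = 36%.
- Placebo loses 10, of whom 5 had recovered: 13/50 = 26%. Fisher's exact p = 0.39.
- Worst case, placebo loses 10 who had all recovered: 8/50 = 16%. Fisher's exact p = 0.039; uncorrected chi-square p = 0.023. Both are below 0.05.

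The reverse also holds. If completers show 20/50 in each arm (no difference), the difference over all randomised could lie anywhere from 20/60 − 30/60 = −16.7 to 30/60 − 20/60 = +16.7 percentage points.

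**Why a missing-data rule is needed as well.** In the worst case, counting all leavers as not recovered gives 18/60 = 30% v 8/60 = 13.3%, Fisher p = 0.045. The false difference is still there. If recoveries reported in the bi-weekly surveys before exit are counted, and all of them were reported, the comparison returns to 18/60 v 18/60. So restoring the denominator is not enough: data up to exit and a sensitivity analysis are needed too.

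**Whether the top-up has to be run by arm.** Pooled attrition of one in six with 1:1 randomisation continued also gives 120 in total, 60 per arm. With 60 per arm and 16.7% dropout in each, the completer counts differ by 6 or fewer in about 89% of simulated trials. For assumed rates of 30% v 50% (two-sided 0.05), power is 53.3% at 50/50 and 53.0% at 47/53. Exact balance among completers gains almost nothing.

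**The case against.** The plan never says that only completers are analysed. A figure for the final analysis can be a planning target, Section 14.0 retains data up to withdrawal, and the bi-weekly surveys give most dropouts some outcome data. This stands in part: a completers-only analysis is an inference. But keeping data is not the same as analysing them, and the sizing and the removal rule both point the other way.

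Section 17.1 says the study is not powered, so having fewer than 50 in an arm breaches no stated power target. That also stands. The table above shows a planning shortfall, not a bias. The p = 0.04 example is a deliberate worst case at an assumed recovery rate, and the milder one is far from significant. Attrition can still be counted, because Section 6.2 records discontinuations in a dedicated survey.

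A reader might infer more from the per-arm wording: that the top-up needs attrition to be watched by arm, directs new subjects to the depleted arm and so defeats concealed allocation in a trial described with "This is a double-blind, randomized controlled trial (RCT) with two treatment arms". The documents do not support this. They state no arm-level trigger and no steering, and Section 6.2 says only that "Subjects will be randomly assigned to receive 3 Omega-3 (EPA+DHA) mini-capsules twice daily" or placebo. Pooled attrition with 1:1 allocation produces the same 60 per arm. The written route by which arms become known during the trial is different: Section 8.0 discloses the arm at dropout for an adverse event and within four weeks of each completion, while Section 9.0 shows enrolment running over Months 4 to 8. That is a separate matter from the sample size.

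**Conclusion.** The concern holds as a gap in the definition of the analysis, and it should be fixed. The sizing, the removal of non-compliers and the missing analysis set together lead to a comparison of those who remain, which is open to bias whenever reasons for leaving differ by arm. At the plan's maximum, up to 20 of 120 randomised subjects (16.7%) could be left out. Under an assumed 30% recovery, no true effect and 10 lost per arm, the spurious difference is 10 percentage points in the milder illustration and 20 in the worst case. Only the worst case crosses the plan's threshold. How large any bias would be in practice cannot be known from the documents. No sample-size sum is wrong, and the documents do not show that the top-up compromises allocation.

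**What to change.** In Sections 1.0, 12.0 and 17.1:

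- State that all randomised subjects are compared in their assigned arm, including those removed for non-compliance, using all bi-weekly data up to exit.
- State the rule for missing week-12 recovery, for example counted as not recovered, and how a recovery reported before exit is treated. Add a sensitivity analysis, and give the completers' comparison as secondary.
- Base any top-up towards 120 on pooled attrition only, with 1:1 randomisation continued and no replacement by arm. Fixing one number to randomise in advance would also be sound, but is not necessary.
- Report week-12 retention by arm, over all randomised, as a feasibility result.
- State that 100 subjects with week-12 data out of 120 assumes overall attrition of at most 16.7%.

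The cost is protocol wording and a short sensitivity analysis, with no subjects beyond the existing maximum. The downside is that 50 per arm with week-12 data is no longer assured, and an arm may fall below it.
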